12.3.3.4 Missing Data Handling

[figure not shown]
For the primary analysis of the primary endpoint, missing data will be assumed to be missing at random conditional on the observed data and covariate; consequently, no imputation of missing data will be performed.

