7.2 Sample Size and Power

The primary efficacy endpoint is percent reduction from baseline in cough frequency (cough events per day) to the average of Week 8 through Week 12. Assuming a standard deviation of 1 for the log ratio of cough frequency post-baseline versus baseline, a sample size of approximately 100 subjects will provide 95% confidence intervals (which represents the estimation precision) as shown in Table 7-1 at various observed percent reductions in cough frequency (30%, 40%, and 50%), after accounting for 20% missing. Note: percent reduction equals $100\% \times (1 - \text{ratio of cough frequency post-baseline vs. baseline})$.

Table 7-1 95% Confidence Intervals for Percent Reduction in Cough Frequency per day from Baseline

Percent reduction in cough frequency	30%	40%	50%
95% Confidence Intervals	(13%, 44%)	(25%, 52%)	(38%, 60%)

30%, 40%, 50% percent reduction corresponds to ratio of 0.7, 0.6 and 0.5 in cough frequency (post-baseline vs. baseline), respectively.

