9.3.1.2 Primary Analysis

The primary endpoint is the percent reduction from baseline in cough frequency (cough events per day) to the average of Week 8 through Week 12. The primary analysis will be based on a mixed-effects model for repeated measures (MMRM) with change from baseline at each post-baseline visit (Week 2 to Week 12) on the natural log scale (i.e., $\log(\text{post-baseline}) - \log(\text{baseline})$) as the dependent variable. Note that if cough frequency is zero at any visit, 0.5 will be added in order to ensure a non-zero number for appropriate natural log calculations. The model will include visit as a fixed effect and log baseline cough frequency as a covariate. The model will be estimated using restricted maximum likelihood. Denominator degrees of freedom for the F-test for fixed effects will be estimated using the Kenward-Roger approximation.³ An unstructured covariance structure will be used to model the within-subject errors. If the model estimation does not converge, a compound symmetry covariance structure will be used instead. Conditional on the observed data and covariates, missing data will be assumed to be missing at random; no additional imputation of missing data will be performed.

The primary result obtained from the model will be the estimated percent reduction in cough frequency from baseline to the average of Week 8 through Week 12 (defined as the average of Weeks 8, 9, 10, 11, 12). Percent reduction will be calculated as $100\% \times (1 - \text{exponential form of LS mean change at the average of Weeks 8 through 12 on the natural log scale from the above MMRM model})$. The 2-sided 95% confidence intervals will be provided. Furthermore, the estimated percent reduction at each post-baseline week will also be provided. The estimated percent reduction at each post-baseline week up to Week 12 will be plotted.

The geometric mean and geometric SD of the raw values at baseline and each post-baseline visit up to Week 12 will also be summarized. In addition, daytime and overnight cough frequency per hour will be summarized in a similar way. If the daytime or overnight cough frequency per hour is zero at a given visit, 0.5/24 will be added to ensure a non-zero number.

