9.3.2.2 Analysis Method

The analysis will be based on an MMRM model similar to the analysis of the primary efficacy variable (without any natural log transformation), with change from baseline at each post-baseline weekly interval (Week 1 to Week 12) as the dependent variable. The model will include the weekly intervals as fixed effects and baseline total step count per day as a covariate.

The primary result obtained from the model will be the estimated mean change from baseline to the average of Week 8 through Week 12. The estimated mean change and 2-sided 95% confidence interval will be provided. Furthermore, the estimated mean change at each post-baseline weekly interval will also be provided. The estimated mean change at each post-baseline weekly interval up to Week 12 will be plotted.

[figure not shown]
In addition, the post-baseline raw values and the change from baseline at each post-baseline weekly interval up to Week 12 will be summarized descriptively (n, mean, SD, median, minimum, and maximum).

[figure not shown]

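### The primary MMRM does not say where its single-arm LS mean is evaluated and fits one baseline slope for all visits, so the Week 8–12 result can be biased if missingness depends on baseline cough

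*SAP*

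**What the plan says.** The dependent variable in SAP 9.3.1.2 is "change from baseline at each post-baseline visit (Week 2 to Week 12) on the natural log scale", which gives 11 visits. The mean model is stated in one sentence: "The model will include visit as a fixed effect and log baseline cough frequency as a covariate". Estimation is by REML with Kenward-Roger degrees of freedom and an unstructured covariance. The headline figure is 100% × (1 − exp(LS mean)), with the LS mean averaged over Weeks 8 to 12. Protocol 12.3.3.1 has the same main-effects form and leaves detail to the SAP.

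Neither document includes a baseline-by-visit term. Neither says at which baseline value, or over which subjects or records, the LS mean is taken. SAP section 4 names SAS as the software but gives no setting for this.

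On missing data, Protocol 12.3.3.4 states that "missing data will be assumed to be missing at random conditional on the observed data and covariate", and nothing is imputed. SAP 7.2 states its precision "after accounting for 20% missing". The step-count model in SAP 9.3.2.2 has the same structure: "The model will include the weekly intervals as fixed effects and baseline total step count per day as a covariate".

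**The concern.** In a two-arm trial, the covariate value at which LS means are evaluated cancels from the treatment difference when both arms share a slope. Here there is one arm and the LS mean is the answer, so both the evaluation point and the fitted slope enter the reported percent reduction directly.

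Two separate weaknesses follow.

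- **Evaluation point.** If the covariate mean is taken over the records in the model, a subject with all 11 valid visits counts 11 times and one who stops after the first counts once. When missingness is related to baseline, that mean drifts away from the mean of the enrolled subjects.
- **Common slope.** Missing at random protects the estimate only if the mean model is right at each visit. If the relation between log change and log baseline differs between early visits and Weeks 8 to 12, a pooled slope adjusts wrongly for the subjects who are missing late.

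At stake are a few points on the primary result, in a direction the plan cannot predict. More data from the same process would not shrink this error.

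**Working it through.** **1. The plan's own figure.** From SAP 7.2: SD 1 on the log scale, 100 subjects, 20% missing, so n = 100 × 0.8 = 80 and SE = 1/√80 = 0.112. The interval is 100% × (1 − ratio × exp(±1.96 × 0.112)). For ratios 0.7, 0.6 and 0.5 this gives (12.9, 43.8), (25.3, 51.8) and (37.8, 59.8). These round to the stated (13, 44), (25, 52) and (38, 60). The table is correct and is not affected by this point.

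**2. When the issue vanishes.** With complete data every subject has the same number of records, so the record mean equals the subject mean. The LS mean at that value is then the plain visit mean, whatever the slope.

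**3. Evaluation point, by formula.** Shift in the LS mean = slope × (record-level mean − subject-level mean of log baseline). It needs only a non-zero slope. A negative slope is plausible: the response subtracts log baseline, and baseline normally rests on two 24-hour recordings (SAP 9.3.1.1), so regression to the mean alone would produce one. Example from the dropout runs below at g = 1: the record mean lay 0.108 SD below the subject mean and the fitted slope was −0.39. The shift is 0.39 × 0.108 = 0.042 log, and 1 − 0.5 × exp(0.042) = 47.9%, which agrees with the table.

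**4. Simulation.** Assumptions that are not in the documents: log-baseline SD 1, total SD 1 per visit, residual correlation 0.6, true reduction 50%, 20% missing at Weeks 8–12, n = 40,000. High-cough subjects go missing, with log-odds g per SD of log baseline; g = 0.5, 1 and 2 are odds ratios of 1.65, 2.7 and 7.4. Entries are the percent reduction from the planned main-effects model.

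| Slope, Week 2 → Weeks 8–12 | Evaluated at | Missingness | g = 0 | 0.5 | 1 | 2 |
|---|---|---|---|---|---|---|
| −0.4 throughout | subject mean | dropout | 50.0 | 50.1 | 50.1 | 50.0 |
| −0.4 throughout | record mean | dropout | 50.0 | 48.9 | 47.9 | 46.7 |
| −0.4 throughout | record mean | intermittent | 50.0 | 48.0 | 46.3 | 44.5 |
| −0.2 → −0.5 | subject mean | dropout | 50.0 | 49.2 | 48.6 | 47.7 |
| −0.2 → −0.5 | subject mean | intermittent | 50.0 | 49.6 | 49.3 | 48.3 |
| 0 → −0.6 | subject mean | dropout | 49.9 | 48.9 | 47.6 | 46.2 |
| 0 → −0.6 | subject mean | intermittent | 50.0 | 49.5 | 49.0 | 48.0 |
| −0.6 → 0 | subject mean | dropout | 50.0 | 51.9 | 53.2 | 54.6 |
| −0.6 → 0 | subject mean | intermittent | 50.0 | 50.7 | 51.3 | 51.8 |

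With a baseline-by-visit term and the subject-level mean, every dropout scenario gave 49.9% to 50.1%, and so did the intermittent ones up to g = 1. At g = 2 with intermittent gaps, 0.3 to 0.7 points remained. With equal slopes the figure there was 49.5%: ln(0.505/0.500)/0.41 = 0.024 SD. That is consistent with subjects who have no valid post-baseline recording falling out of the averaged baseline, and it is why the fix specifies all FAS subjects with a valid baseline.

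**5. Range used for the verdict.** Further runs at odds ×1.5 to ×2.5 per SD gave about 1 to 4 points at the record mean (slopes −0.3 to −0.5 at Weeks 8–12, dropout or intermittent). They gave about 0.3 to 2.6 points at the FAS mean when slopes changed. The g = 2 column is an extreme beyond this range.

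**6. At the planned N = 100** (300 replicates, dropout, slopes −0.2 → −0.5, g = 1): 48.7% at the subject mean, 46.6% at the record mean, and 50.1% with the interaction. Interval coverage was 0.87, 0.79 and 0.89. These intervals used maximum-likelihood standard errors without Kenward-Roger and ran low for all models, so only the contrast is informative.

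**7. Scale.** On the log scale, 1 and 4 points at 50% are ln(51/50) = 0.020 and ln(54/50) = 0.077, or 0.18 and 0.69 of the planning SE of 0.112. Likewise 0.3 and 2.6 points are 0.006 and 0.051, or 0.05 and 0.45 of that SE.

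**The case against.** A reader might infer that 20% missing data makes the planned estimate biased even under missing at random. The documents do not support that. The 20% is an allowance in a precision table, with no pattern and no link to baseline. The g = 0 column shows no bias when missingness is unrelated to baseline. With equal slopes and evaluation at the FAS mean there is none either.

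It is also tempting to argue that the slope must change because the drug effect builds up over time. That does not follow: the visit effect already lets the mean change freely, and no section gives a baseline slope or its time course.

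The 20% need not be monotone dropout. Each 24-hour recording is judged valid or not by itself (SAP 9.3.1.1), and Protocol 5.1 reports few treatment discontinuations on this regimen. Under intermittent missingness the slope component is usually about 1 point or less for odds up to ×2.5. The study is also estimation-only, the interval at 50% runs from 38% to 60%, and geometric means by visit will be reported alongside.

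All of this stands, and it makes the interaction the lesser item. It does not remove the evaluation-point gap, which persists under intermittent missingness, which the interaction alone does not cure, and which leaves the primary number open to more than one calculation.

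**Conclusion.** The point holds conditionally. SAP 9.3.1.2 has one baseline slope and no stated evaluation point. The missing-at-random assumption it relies on allows missingness to depend on baseline cough. If it does, at a true reduction of 50%:

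- (a) a record-level covariate mean shifts the Week 8–12 result by about 1 to 4 points, given any non-zero slope in the assumed range;
- (b) a slope that changes over visits shifts it by about 0.3 to 2.6 points even at the FAS mean, less if missingness is intermittent.

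With a negative slope, loss of high-cough subjects makes (a) understate the reduction, and loss of low-cough subjects makes it overstate. For (b) the sign also depends on how the slope moves. The documents neither establish nor exclude these conditions, and they do not say that a record-level mean will be used. No bias was simulated for step count, so none is claimed there. This is a cheap improvement, held with moderate confidence.

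**What to change.** In SAP 9.3.1.2, in this order:

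1. State that the LS means and the Week 8–12 contrast are evaluated at the mean log baseline of all FAS subjects with a valid baseline, each subject counted once, whether or not they have valid post-baseline recordings.
2. Add the log baseline-by-visit interaction to the fixed effects.

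Use the same form in SAP 9.3.2.2, with baseline steps by weekly interval, for consistency.

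The cost is two sentences in the SAP, 10 extra fixed-effect parameters for cough (11 slopes in place of 1) and 11 for steps (12 in place of 1), and about 1 to 2% of precision. In one simulation at n = 100 the estimator's SD rose from 0.102 to 0.104. The sample size and SAP Table 7-1 do not change. The first item costs no precision and also makes the primary figure reproducible whatever the missingness pattern.

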11.2.1 Cough Measurements

[figure not shown]
Subjects will be provided with a non-invasive, semi-automated, ambulatory cough monitoring system to record cough frequency. The system will be used for a single day (defined by 24 continuous hours) at time points specified in Table 3-2. Subjects will put the cough device on under direct observation at the time of contact between the subject and investigator or site personnel (i.e., in person or telemedicine contact).

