9 STATISTICAL ANALYSIS

9.1 General Considerations

Continuous variables will be summarized using the following descriptive summary statistics: the number of subjects (n), mean, SD, median, minimum value (min), and maximum value (max).

Categorical variables will be summarized using counts and percentages.

Baseline value, unless specified otherwise, will be defined as the most recent non-missing measurement (scheduled or unscheduled) collected before the first dose of study drug.

Absolute change from baseline will be calculated as post-baseline value – baseline value.

Relative change from baseline will be calculated and expressed in percentage as $100\% \times (\text{post-baseline value} - \text{baseline value}) / \text{baseline value}$.

Treatment-emergent (TE) Period will include the time from the first dose of study drug to 28 days after the last dose of study drug or to the completion of study participation, whichever occurs first.

Incomplete/missing data will not be imputed, unless specified otherwise.

Unscheduled visits: Unscheduled visit measurements will be included in analysis as follows:

- 1) In scheduled visit windows per specified visit windowing rules
- 2) In the derivation of baseline and last on-treatment measurements
- 3) In the derivation of maximum and minimum values during TE period, and maximum and minimum change from baseline values during TE period for safety analyses
- 4) In individual subject data listings as appropriate

Visit windowing rules: The analysis visit windows for protocol-defined visits are provided in Appendix A.

Outliers: No formal statistical analyses will be performed to detect or remedy the presence of statistical outliers, unless specified otherwise.

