9.3.1 Analysis of Primary Efficacy Variable

9.3.1.1 Definition of Variable

The primary endpoint is percent reduction from baseline in cough frequency (cough events per day) to the average of Week 8 through Week 12. Percent reduction from baseline will be calculated and expressed in percentage as $100\% \times (\text{baseline value} - \text{post-baseline value}) / \text{baseline value}$ (i.e., -relative change)

Cough frequency per day will be measured by a non-invasive, semi-automated, ambulatory cough monitoring system. The device will be used for a single day (defined by 24 continuous hours) at visits specified in Table 3-2 in CSP. The 24-hour assessment is considered valid if there are at least 10 cumulative hours of recording duration while awake, excluding any duration where the recording is identified as muted, flagged, or device not attached, and excluding any duration where the recording ended early.² For valid assessments, the cough frequency per day is the total number of cough events in the 24-hour period (excluding any duration where the recording is identified as muted, flagged, or device not attached, and excluding any duration where the recording ended early).

The baseline value is defined as the geometric mean of valid cough measurements prior to the first dose of study drug (e.g., Day -14 and Day -7). If one value is missing or invalid, the non-missing, valid value will be used. If the cough frequency is zero at a given visit, 0.5 will be added to ensure a non-zero number.

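### Does the absence of a minimum overnight recording time spoil the overnight cough-per-hour summary?

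*SAP*

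**What the plan says.** The cough device is meant to run for one full day at each time point. SAP 9.3.1.1: "The device will be used for a single day (defined by 24 continuous hours) at visits specified in Table 3-2 in CSP". Protocol 11.2.1 adds how it starts: "Subjects will put the cough device on under direct observation at the time of contact".

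Validity rests on waking time. SAP 9.3.1.1: "The 24-hour assessment is considered valid if there are at least 10 cumulative hours of recording duration while awake". Lost time is removed from both the validity check and the count: "excluding any duration where the recording is identified as muted, flagged, or device not attached, and excluding any duration where the recording ended early".

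The primary model in SAP 9.3.1.2 uses the total count per day. After it come the descriptive summaries: "The geometric mean and geometric SD of the raw values at baseline and each post-baseline visit up to Week 12 will also be summarized". The day and night rates take one further sentence: "In addition, daytime and overnight cough frequency per hour will be summarized in a similar way". The zero rule "If the daytime or overnight cough frequency per hour is zero at a given visit, 0.5/24 will be added to ensure a non-zero number" follows. It is the daily rule (0.5 events per day) expressed per hour.

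Three general rules bear on the point. SAP 9.1 does not impute missing data unless stated otherwise. SAP Appendix A (note 3 to Table 12-1) treats a visit with no numerical value in its window as missing. On extreme values SAP 9.1 says: "No formal statistical analyses will be performed to detect or remedy the presence of statistical outliers, unless specified otherwise".

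**The concern.** The daytime rate is protected by the 10-hour rule. The overnight rate has no such floor. With a daytime contact, the night falls late in the 24 hours, so a recording can already hold its 10 waking hours and then stop early in the night. It stays valid, and the overnight part may last an hour or less.

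A short record is more likely to be silent by chance, and any zero becomes the same 0.0208 per hour whether it stands for one hour or eight. A geometric mean is sensitive to very small values, and no weighting by recorded time is stated. Device failure could then look like a quiet night. If failures were more common after baseline than before it, the table could suggest an overnight improvement that did not occur, in a single-arm open-label study whose subject is cough reduction.

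**Working it through.** **1. What the plan's own figures depend on.** The constant is 0.5/24 = 0.0208 per hour. The only precision figures, in SAP Table 7-1, concern the daily count. With 100 × 0.8 = 80 evaluable subjects and log SD 1, a 30% reduction has limits 1 − 0.7 × exp(±1.96/√80) = 12.9% and 43.8%, which match the table's 13% and 44%. Overnight rates do not enter this or the primary model.

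**2. The mechanism.** Assume Poisson counts, so P(silent) = exp(−rate × hours).

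| True rate per hour | Silent in 1 h | Silent in 8 h |
|---|---|---|
| 0.5 | 61% | 1.8% |
| 1 | 37% | 0.03% |
| 4 | exp(−4) = 1.8% | negligible |

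One cough in a record of h hours scores (1/h)/(0.5/24) = 48/h times a silent one: 6 times for 8 h and 48 times for 1 h. The mechanism exists, but its strength depends on a cough rate that the documents do not give.

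**3. An extreme illustration.** Assume a median of 1 per hour, between-subject log SD 1 and 8-hour nights. With all nights full, the geometric mean is 0.890 and the geometric SD 3.44. If 5/10/20% of nights held exactly 1 h, the mean would be 0.849/0.810/0.738 (5/9/17% lower) and the SD 3.76/4.07/4.71. If the short nights held 4 h, the mean would be 0.7/1.5/2.9% lower.

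**4. How many valid nights could be that short?** Assume contact at 13:00 and a night from 23:00 to 07:00. The 24 hours are then 10 waking, 8 overnight and 6 waking. A recording that stops at hour 10 or later is valid. Let a share f stop early, uniformly over the 24 hours.

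- Valid share: (1 − f) + f × 14/24. For f = 0.20 this is 0.917.
- Valid records with 1 overnight hour or less: (0.20 × 1/24)/0.917 = 0.9%.
- Valid records with any partial night: (0.20 × 8/24)/0.917 = 7.3%.
- For 5% of valid records to hold 1 h or less: f/24 = 0.05 × (1 − 10f/24), so f = 0.80.
- Upper limit, f = 1: (1/24)/(14/24) = 7.1%. Shares of 10% or 20% cannot occur under this pattern.

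A contact later than 13:00 leaves fewer than 10 waking hours before the 23:00 bedtime. A recording that ended during the night would then fail the 10-hour rule, so the rule gives the night some indirect protection.

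**5. Effect with f = 0.20.** Average the change in mean log rate over partial nights of 0 to 8 recorded hours, with rates on recorded hours and zeros set to 0.0208.

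- Median 1 per hour: average change −0.396, so the geometric mean is multiplied by exp(−0.0727 × 0.396) = 0.972 (2.8% lower). The geometric SD goes from 3.44 to 3.63.
- Median 4 per hour: average change −0.207, so the factor is exp(−0.0727 × 0.207) = 0.985 (1.5% lower).

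If the code instead divided by a nominal 8 hours, the average changes would be −1.03 and −1.05, and the mean about 7% lower (exp(−0.0727 × 1.03) = 0.928). A rate per hour from a recording whose lost time has been removed is naturally taken over the hours that remain.

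**6. A night with no recording.** With recorded hours as divisor the rate is 0/0, which is undefined and not zero. Unrecorded time is excluded under SAP 9.3.1.1, and SAP 9.1 does not impute. The zero rule applies to an observed zero. Reading an empty night as 0.5/24 would contradict these rules, so no size is given for that case.

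**The case for a change.** The best case for a change is that the SAP applies minimum-duration rules elsewhere: 10 waking hours for cough, and for steps 10 waking hours of wear with at least 3 valid weekdays and 1 weekend day per interval. The overnight rate alone has none. For silent records the error has a direction, since lost recording reads as less cough. Early stops need not be uniform either: subjects who remove or mute the device soon after going to bed would produce more short nights than step 4 allows. Two sentences and a filter would settle it.

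Part of this stands. The omission is genuine in the visible text, and clustering after bedtime could raise the share of short nights toward the extreme illustration. But the documents give no sign of it, and removal at bedtime itself leaves no overnight data, which is a missing value. Part of the SAP after 9.3.2 is redacted, so period definitions may exist where they cannot be read. Any minimum would also be a judgement: it would discard partial nights that carry information, to protect a table from which no formal inference is drawn.

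**Conclusion.** No change follows. The visible text of SAP 9.3.1 leaves open the overnight window, the divisor and a minimum recorded time, and a short silent night would enter at 0.0208 per hour. Analysts have to settle the first two to program the table, and the sensible choices (valid recorded hours; a night without recording is missing) follow from rules the SAP already states. Equal weight per subject is normal for a descriptive geometric mean.

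The likely size is about 1–3% of the overnight geometric mean if 20% of recordings stop early at uniform times. This rests on assumed Poisson counts, log SD 1, 8-hour nights, median rates of 1 to 4 per hour, the clock times above and a recorded-hours divisor. The 5–17% figures require 5–20% of valid nights to hold a single hour, which is an extreme case. The primary model, the step-count endpoint and the planned precision are untouched whichever case applies, and no test, confidence interval or decision uses the overnight rates.

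### Is 0.5/24 the wrong substitute for a zero daytime or overnight hourly cough rate?

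*SAP*

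**What the plan says.** SAP 9.3.1.1 defines the main variable as a daily count: "the cough frequency per day is the total number of cough events in the 24-hour period". For a zero it adds half an event: "If the cough frequency is zero at a given visit, 0.5 will be added to ensure a non-zero number". SAP 9.3.1.2 repeats this for the log-scale model: "Note that if cough frequency is zero at any visit, 0.5 will be added in order to ensure a non-zero number".

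The same section then turns to the parts of the day: "In addition, daytime and overnight cough frequency per hour will be summarized in a similar way". The preceding sentence asks for the geometric mean and geometric SD of the raw values, so these rates are also summarised on a log scale and a zero needs a substitute. The rule is: "If the daytime or overnight cough frequency per hour is zero at a given visit, 0.5/24 will be added to ensure a non-zero number". One constant serves both periods.

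The visible text gives no lengths for daytime and overnight and no reason for the divisor. It sets a minimum only for awake recording: "valid if there are at least 10 cumulative hours of recording duration while awake".

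**The concern.** A zero in the 24-hour count is replaced by half an event over the window observed. If that is the principle, a zero over a period of T hours should become 0.5/T per hour. The SAP divides by 24 for periods that cannot last 24 hours, so its substitute is T/24 of that value: one third for an 8-hour night and two thirds for a 16-hour day.

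On a log scale this is not trivial. Each silent night would enter ln 3 = 1.10 units lower than under 0.5/T, which pulls the overnight geometric mean down and widens its geometric SD. The treatment is meant to reduce cough, so silent nights may become more frequent after baseline. The low substitute would then exaggerate the overnight fall, in a single-arm study with no control group to offset it.

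**Working it through.** **Inputs.** From the SAP: 0.5 for a zero 24-hour count, and 0.5/24 for a zero hourly rate. Assumed, because the documents give no values: night length (8 h, range 6 to 10 h), day length (16 h), shares of zero nights, and the distribution of counts.

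**1. The plan's own figure.** 0.5 events per day ÷ 24 hours per day = 0.0208 events per hour. The constant is reproduced exactly as the daily floor in hourly units.

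**2. The gap to a half-event rule.** (0.5/24) ÷ (0.5/T) = T/24, and the log gap is ln(24/T).

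| T (h) | 0.5/T per hour | T/24 | ln(24/T) |
|---|---|---|---|
| 6 | 0.0833 | 0.25 | 1.39 |
| 8 | 0.0625 | 0.33 | 1.10 |
| 10 | 0.0500 | 0.42 | 0.88 |
| 16 | 0.0313 | 0.67 | 0.41 |

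This arithmetic is right. It shows that the two rules differ, not which one is wrong.

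**3. Which rule agrees with the daily floor?** Take a fully recorded, silent 24 hours split into 16 h of day and 8 h of night, and convert the two substituted rates back to events per day.

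- SAP rule: 16 × 0.5/24 + 8 × 0.5/24 = 0.333 + 0.167 = 0.5, which is the SAP's substitute for a zero day.
- 0.5/T: 16 × 0.5/16 + 8 × 0.5/8 = 0.5 + 0.5 = 1.0, which is twice that substitute.

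The same holds for any split of the 24 hours. As a rate floor, the SAP's constant is the consistent one.

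**4. Does a silent period stay lowest?** One cough in T hours is 1/T, which is at least 1/24 and so always above 0.5/24. Under the SAP rule a silent period therefore ranks below every period with a cough. Under 0.5/T it need not:

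- A silent 8-hour night (0.5/8 = 0.0625) ties with a 16-hour day with one cough (1/16 = 0.0625).
- A silent 2-hour overnight recording (0.5/2 = 0.25) ranks above an 8-hour night with one cough (1/8 = 0.125). The SAP sets no overnight minimum that would exclude it.

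**5. Is the overnight fall overstated?** Simulation of an 8-hour night with lognormal subject means. Counts are either Poisson, or Poisson with an added gamma night-to-night factor (shape 1). The table gives the multiplier on the post/baseline ratio of geometric means. A value of 1 is unbiased, below 1 overstates the fall, and above 1 understates it.

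| Model | Zero nights, baseline to post | SAP rule | 0.5/T |
|---|---|---|---|
| Poisson, log-SD 1 | 2% to 10% | 0.90 | 0.98 |
| Poisson, log-SD 1 | 2% to 22% | 0.84 | 1.04 |
| Poisson, log-SD 1 | 2% to 38% | 0.85 | 1.26 |
| Poisson, log-SD 1.5 | 1.5% to 22% | 0.88 | 1.11 |
| Gamma shape 1, log-SD 1 | 7% to 21% | 0.96 | 1.12 |
| Gamma shape 1, log-SD 1 | 7% to 36% | 1.02 | 1.40 |

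The first multiplier is 0.822/0.909 = 0.90 against 0.916/0.933 = 0.98, each term being a geometric mean divided by its true value. The third is 0.771/0.909 = 0.85 against 1.173/0.933 = 1.26. In the gamma rows the night-to-night factor acts equally before and after baseline, so it cancels from the true ratio. Those rows move by about 0.01 between runs.

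The SAP rule is further from 1 in the first two rows. The two are about equally off in the fourth, and 0.5/T is further off in the other three.

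**The case for a change.** The best case for the concern is this. The SAP never says that 0.5/24 is meant as a common rate floor. Read as one, it still credits an 8-hour silent night with only 8 × 0.5/24 = 0.17 events. Under a Poisson model with few zero nights, 0.5/T is closer to the truth at a single visit: at 10% zeros the geometric mean is 0.82 of its true value under the SAP rule and 0.92 under 0.5/T. At 22% zeros the geometric SD is 4.0 against 2.8, where the true value is 2.7. At a single visit, 0.5/T stops being the closer rule only at about 30% to 51% zeros for an 8-hour night, depending on spread.

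Those figures stand under their assumptions, and so does the remark that the SAP gives no reason for its divisor. They do not make the constant an error. The half-event-per-period convention that it is said to break appears nowhere in the plan. The advantage for change on treatment reverses once nights vary within a subject, or once zeros become common. The documents support neither count model over the other.

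Counts of zero nights and days beside the summaries would show a reader how much rests on the substitute. That is an additional table row, not a correction, and it is useful whichever constant is used.

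**Conclusion.** The concern does not hold. The divisor of 24 is the number of hours in a day, used to carry the daily floor of 0.5 over to an hourly scale. It is not a mistaken length for the night. The difference from 0.5/T is real: a factor of 3 per silent 8-hour night, and 4 to 2.4 for nights of 6 to 10 hours. But it separates two defensible conventions. The SAP's choice agrees with its own daily floor and always ranks a silent period lowest. The alternative does neither, and in several plausible settings it biases the overnight change more.

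The consequence is also confined. The constant enters only a descriptive summary of daytime and overnight rates, for which no test is visible. The primary MMRM uses the 24-hour count with the separate 0.5 rule and is untouched.

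That the constant equals the daily floor is exact. That neither rule is better throughout rests on assumed night lengths, zero shares and count distributions. Part of the SAP's efficacy section is redacted, so definitions of day and night that are not visible cannot be taken as missing.
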